⁴ The MRI performed at the end of the LITT procedure may be used as the Discharge Visit MRI.

⁵ See Appendix D for details about the Engel and ILAE surgical outcome classifications.

Table 2: Visits and Testing Requirements and Data Collection Summary (Month 12 through Month 24)

Visit Window	Months 13, 14, 15, 16, & 17	Month 18	Months 19, 20, 21, 22, & 23	Month 24	Early Withdrawal
	± 7 days	± 14 days	± 7 days	± 14 days	
Visit Type					
QOLIE-31		✓		✓	✓
Medication review (epilepsy and non-epilepsy)	✓	✓	✓	✓	
Neurological exam		✓		✓	✓
Functional assessment		✓		✓	✓
Seizure diary	C/D	C/D	C/D	C	✓
Adverse event monitoring	✓	✓	✓	✓	✓
Surgical outcome classifications ¹		✓		✓	✓
Subject satisfaction		✓		✓	✓
Neuropsychological testing ²					✓

Abbreviations: C; collect; D, dispense; QOLIE-31, Quality of Life in Epilepsy - 31; U, update.

¹ See Appendix D for details about the Engel and ILAE surgical outcome classifications.

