7.8 Early Withdrawal/Premature Discontinuation of Subjects

Subjects may be withdrawn early from the study for a number of reasons, including:

- Subjects experiencing a failed LITT treatment attempt. A failed LITT treatment attempt is defined as stopping the procedure prior to thermal delivery. (Subjects that experience a failed treatment attempt will be followed for 1 month post-procedure for related adverse events.)
- Subject death
- Subject lost to follow-up
- Subject request for withdrawal
- Adverse events
- Investigator decision (other than an adverse event)

If a study subject is discontinued from the study early, a Study Completion CRF must be completed describing the reason for early discontinuation. The investigator should make all attempts to conduct an Early Withdrawal visit at the time of withdrawal from the study. If a subject has withdrawn consent for the study or is lost to follow-up, the completion of this visit is not imperative. In situations where study withdrawal is due to an adverse event, subjects will be followed until resolution of the adverse event or determination that the subject's condition is stable.

At the Early Withdrawal visit, the subject will undergo the following evaluations:

- QOLIE-31. It is preferred that the subject completes the questionnaire prior to any other tests.
- Neurological exam (cranial nerves (including confrontation visual field testing), motor, coordination, reflexes, gait, sensation)
- Neuropsychological testing
- Adverse event monitoring
- Subject satisfaction
- Functional assessment (including employment status, education, living arrangements, driving status)
- Surgical outcome classifications (Engel and ILAE, see Appendix D)

If a subject chooses to withdraw from the study and also withdraws consent for disclosure of future information, no further evaluation(s) should be performed and no additional data will be collected. The Sponsor may retain and continue to use any data collected prior to the withdrawal of consent.

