The purpose of this Statistical Analysis Plan (SAP) is to document analyses that are planned for the FLARE study before they are performed (*pre-specified analyses*). The results of the analyses documented here are to be presented in the clinical study final report. Selected analyses may also be presented in interim reports, DSMB reports, and manuscripts reporting study results, as deemed appropriate by the authors. Additional analyses of the study data beyond the analyses pre-specified in this plan are expected, therefore the Statistical Analysis Plan does not preclude ad hoc analyses that may provide additional useful description of the performance of the investigational device.

2 Scope

This SAP should be read in conjunction with the Clinical Study Protocol (CL10054) and Case Report Forms (MON-CRF-1001 through MON-CRF-1030). Changes to the versions of the Clinical Study Protocol (protocol) and Case Report Forms (CRFs) cited above may necessitate updates to the SAP.

3 Applicable Documents

Document Number	Document Title
CL10054	Monteris FLARE Clinical Study Protocol, Rev A
MON-CRF-1001 through MON-CRF-1030	Monteris FLARE Study Case Report Forms
NAMSA STATSOP-002	Statistics Standard Operating Procedure – Statistical Analysis Plan

4 Software

Statistical analyses, tables, listings, and figures will be primarily produced using SAS statistical software (SAS Institute, Cary, NC), version 9.2 or later, or another validated statistical software package.

5 Abbreviations

The following is a list of abbreviations used in the body of this document.

ADE	adverse device effect
AE	adverse event
AED	antiepileptic drug
BVMT-R	Brief Visual Memory Test – Revised
BNT-60	Boston Naming Test – 60 item version
CEC	Clinical Events Committee
DSMB	Data Safety and Monitoring Board
CRF	case report form
ICF	informed consent form
ICH	International Conference on Harmonization
IDE	Investigational Device Exemption
IQ	intelligence quotient
ILAE	International League Against Epilepsy
LITT	laser interstitial thermal therapy
MRI	magnetic resonance imaging

MTLE	mesial temporal lobe epilepsy
NBS	NeuroBlate® System
QOLIE-31	Quality of Life in Epilepsy – 31 item version
RAVLT	Rey Auditory Verbal Learning Test
SAE	serious adverse event
SOP	standard operating procedures
UADE	unanticipated adverse device effect
USADE	unanticipated serious adverse device effect
VAS	visual analog scale
WAIS-IV	Wechsler Adult Intelligence Scale-IV
WMS-IV	Wechsler Memory Scale-IV

6 Design

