LITT Treatment				✓														
MRI					✓	✓								✓				
Surgical pain VAS						✓	✓											
Surgical outcome classifications ³										✓		✓		✓				✓
Subject satisfaction												✓						✓

Abbreviations: C; collect; D; dispense; DC; discharge; I; initial; LITT; laser interstitial thermal therapy; Mo.; month; MRI; magnetic resonance imaging; QOLIE-31; Quality of Life in Epilepsy - 31; U; update; VAS; visual analog scale.

¹ See Appendix A for details of the neuropsychological testing at each visit. These can be performed on a separate day than the study visit, as long as it is completed within the study window.

² Prior neuropsychological testing may be used for baseline values if the testing was conducted within 6 months prior to the specific baseline visit and there were no significant changes to the subject's AEDs or changes to the subject's clinical condition that may affect cognitive function.

³ See Appendix B for details about the Engel and ILAE surgical outcome classifications.

Table 2: Visits and Testing Requirements and Data Collection Summary (Month 13 through Month 24)

	Months 13, 14, 15, 16, & 17	Month 18	Months 19, 20, 21, 22, & 23	Month 24	Early Withdrawal
Visit Window	± 7 days	± 14 days	± 7 days	± 14 days	
Visit Type					
QOLIE-31		✓		✓	✓
Medication review (epilepsy and non-epilepsy)	✓	✓	✓	✓	
Neurological exam		✓		✓	✓
Functional assessment		✓		✓	✓
Seizure diary	C/D	C/D	C/D	C	
Adverse event monitoring	✓	✓	✓	✓	✓
Surgical outcome classifications ¹		✓		✓	✓
Subject satisfaction		✓		✓	✓
Neuropsychological testing ²					✓

Abbreviations: C; collect; D, dispense; QOLIE-31, Quality of Life in Epilepsy - 31; U, update.
¹ See Appendix B for details about the Engel and ILAE surgical outcome classifications.
² See Appendix A for details of the neuropsychological testing.

9 Sample Size

For this feasibility study, there are no hypothesis tests and therefore sample size is not based on power. Rather, the sample size of 30 subjects is based on providing a sufficiently robust characterization of adverse events and other study endpoints. With a sample size of 30 subjects, adverse events that have a 5% probability per-subject have approximately an 80% chance of being observed in at least one subject in the study. Study results obtained from a sample of 30 subjects will permit planning for the potential range of results that could occur in a larger pivotal trial.

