The primary analysis of seizure frequency will include subjects with at least 70 completed diary days in each 3 month period from procedure through 12 months and at least 140 diary days in each 6 month period from 12 months through study completion. To account for incomplete diary completion, sensitivity analyses may be performed by including subjects with less than the required level of diary completion and by using the number of days with completed diary entries to determine the denominator in the event rate calculation.

Seizure frequency may be further characterized by calculating the *proportion of responders*. A responder is a subject whose seizure frequency in a specified 3-month interval is reduced by $\geq 50\%$ as compared to the 3-month Baseline Phase.

Seizure free days may be further characterized by calculating the percent change in seizure-free days that subjects experience during a specified 3-month interval compared to Baseline. In order to make the 3 month follow-up intervals and the Baseline Phase comparable, the number of days actually recorded will be prorated to an 84-day interval for both intervals. Seizure-free days may also be expressed as a proportion of the number of follow-up days with available diary data.

Freedom from seizures with altered awareness will be reported using Kaplan-Meier curve analysis. Seizures with altered awareness include those categorized as either “impairment of consciousness or responsiveness” or “evolving to a bilateral, convulsive seizure”. The time to event analysis will exclude seizures that occur within the first 4 weeks post-procedure. The event time will be calculated using the earliest post-treatment date of a seizure with altered awareness, as reported in subject diaries. The censoring date will be the last completed diary date for subjects without seizures with altered awareness. The Kaplan-Meier analysis may be repeated for freedom from all seizures, seizures with other classifications, and inclusion of seizures within the first 4 weeks post-procedure. The log-log transformation will be used to calculate 95% confidence intervals. The time point of primary interest is 24 months.

Longest seizure-free interval will be characterized with descriptive statistics for each 3-month period and cumulatively over consecutive 3-month periods. The seizure-free interval will be

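### Protocol Table 2 schedules the seizure diary at Early Withdrawal, but section 7.8 and SAP Table 2 omit it, so a first recurrence in the last diary could be censored instead of counted

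*Protocol*

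**What the plan says.** Three places describe the Early Withdrawal visit.

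- **Protocol 7.5, Table 2.** The diary row reads "Seizure diary C/D C/D C/D C" for the four scheduled columns and then has a tick under Early Withdrawal.
- **Protocol 7.8.** "At the Early Withdrawal visit, the subject will undergo the following evaluations" introduces seven items: QOLIE-31, neurological exam, neuropsychological testing, adverse events, satisfaction, functional assessment, and Engel/ILAE classes. There is no diary.
- **SAP section 8, Table 2.** The diary row has the same four codes and a blank Early Withdrawal cell. SAP section 3 names its source as "Monteris FLARE Clinical Study Protocol, Rev A"; the protocol supplied is Rev B.

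SAP 11.1.3 then makes the diary the only source for the time-to-first-seizure analysis. For events: "The event time will be calculated using the earliest post-treatment date of a seizure with altered awareness, as reported in subject diaries". For everyone else: "The censoring date will be the last completed diary date for subjects without seizures with altered awareness". On the horizon: "The time point of primary interest is 24 months".

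**The concern.** Section 7.8 is the text a coordinator is likely to open when a subject leaves, and it gives a different data-collection instruction from the schedule table in the same protocol. The diary at issue covers the days just before exit. If it is not collected, the Kaplan-Meier analysis has no second source for those days. A subject with no earlier recorded altered-awareness seizure, whose first one (after the excluded first 4 weeks) falls there, leaves the risk set as a censored observation although an event occurred. Censoring that depends on the outcome in this way pushes the seizure-free estimate upwards, and with about 30 treated subjects each case is visible.

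**Working it through.** **1. The texts side by side**

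| Early Withdrawal item | Protocol Table 2 | Protocol 7.8 | SAP Table 2 |
|---|---|---|---|
| Seizure diary | ticked | absent | blank |
| The seven items listed in 7.8 | ticked | listed | ticked |
| Medication review | blank | absent | blank |

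Only the diary differs. The SAP's blank may reflect its Rev A source. The conflict between Table 2 and 7.8 cannot, because both are in Rev B.

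**2. How much diary is at risk**

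Diaries are collected at monthly calls or visits (Protocol 7.6), and SAP 12.3 defines a study month as 28 days.

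- Nominal gap: 28 days.
- Two contacts with ±7-day windows at opposite extremes: 28 + 7 + 7 = 42 days.
- Next to the ±14-day Month 18 or Month 24 visit: 28 + 7 + 14 = 49 days.

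Everything before the last contact has already been collected.

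**3. Effect on the 24-month estimate**

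The plan states no figure for this analysis. Its one sample-size figure, about an 80% chance of seeing a 5% adverse event in 30 subjects, reproduces (1 − 0.95^30 = 78.5%) and is not in dispute; only n = 30 is taken from it.

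Assumptions, none of them in the documents: m other subjects have an event, spread evenly over study months 1 to 12; one subject withdraws with a first seizure only in the final diary; nobody else is lost before day 672 (24 × 28). Let k be the number of the m events that occur before the previous monthly collection, which is where the subject would be censored.

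- Seizure counted: S_E = (n − m − 1)/n
- Subject censored: S_C = [(n − k)/n] × [(n − m − 1)/(n − k − 1)]
- Overstatement: S_C − S_E = (n − m − 1)/[n(n − k − 1)]

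With n = 30 and m = 12, S_E = 17/30 = 56.7%:

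| Withdrawal at month | k | S_C | Overstatement |
|---|---|---|---|
| 3 | 1 | 29/30 × 17/28 = 58.7% | 17/(30 × 28) = 2.0 points |
| 6 | 4 | 26/30 × 17/25 = 58.9% | 17/(30 × 25) = 2.3 points |
| 12 | 11 | 19/30 × 17/18 = 59.8% | 17/(30 × 18) = 3.1 points |
| 18 | 12 | 18/30 = 60.0% | 17/(30 × 17) = 3.3 points |

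Varying m:

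- m = 9, month 3 (k = 0): 20/(30 × 29) = 2.3 points.
- m = 15, month 3 (k = 1): 14/(30 × 28) = 1.7 points.
- Once all other events have occurred, the difference is 1/30 = 3.3 points whatever m is.

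So the range for one affected subject is 1.7 to 3.3 points.

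Three affected subjects with staggered exits (days 100, 190 and 280; 12 other events evenly spaced over days 40 to 520):

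- Censored on those days: 28/30 × 25/27 × 22/24 × 15/21 = 56.6%.
- Counted: 15/30 = 50.0%.
- Difference: 6.6 points, or 2.2 per subject.

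With none affected, the difference is zero.

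**4. Against sampling error**

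For m = 12 and one subject leaving at month 12, the log-log 95% intervals are 40 to 75% (censored) and 37 to 72% (counted). The shift is small beside the interval width, but its direction is always upward.

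**The case against.** The strongest reply is that this is an editorial mismatch. Section 7.5 presents Tables 1 and 2 as the testing requirements, and Table 2 schedules the diary. Appendix B has staff review the diary at each visit, with no exception for Early Withdrawal. SAP section 17 includes all available data from subjects who drop out. Engel and ILAE classes are recorded at this visit in all three places. The outcome is secondary and descriptive.

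Much of that stands. It makes loss of the diary possible, not expected. It does not remove the conflict, because 7.8 reads as a complete list, and the Engel and ILAE classes do not feed the Kaplan-Meier analysis. Worst-case imputation in SAP section 17 could expose the problem, but it is optional.

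Four stronger readings might be inferred, and the documents do not support them:

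- *The last diary is lost and the subject counts as seizure-free.* Loss requires a site to follow 7.8 and overlook Table 2 and Appendix B. Even then the subject is censored at the last completed diary day and is not carried as seizure-free to 24 months. In the month 3 example above, censoring gives 58.7%, whereas carrying the subject as seizure-free would give 18/30 = 60.0%.
- *The seizure rate in the last interval is understated.* Under SAP 12.4, days without diary data leave the denominator; they are not scored as seizure-free. The main frequency analysis also requires 70 diary days in each 3-month period and 140 in each later 6-month period, so an early withdrawal would generally be excluded whether or not the last diary arrives.
- *The missing medication review is part of the contradiction.* It is absent from all three places, so nothing conflicts. Appendix A separately requires prescription medications taken during the trial to be recorded.
- *Recurrence drives withdrawal.* It is plausible, but section 7.8 does not list it as a reason and the documents give no frequency for any reason.

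**Conclusion.** The point holds in limited form. Rev B gives sites two instructions about the only data source for a planned secondary analysis, and the SAP repeats the omission. The consequence is conditional. It needs an Early Withdrawal visit that takes place, a site that follows 7.8 alone, and a first altered-awareness seizure that falls after the last monthly contact. Subjects with an earlier recorded event are unaffected. For each subject who meets those conditions, the 24-month seizure-free estimate is too high by roughly 2 points out of 30 treated (1.7 to 3.3 in the scenarios tried, nearer the top for later exits). Those sizes rest on assumed event counts, timing and withdrawals; the number affected may be zero. The text mismatch is certain and the bias is not. It merits correction because the remedy costs almost nothing.

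**What to change.** Reconcile the three passages in line with Protocol Table 2:

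1. Add seizure diary collection to the Early Withdrawal list in Protocol 7.8.
2. Mark diary collection in the Early Withdrawal column of SAP Table 2 when the SAP is updated to Rev B. Using the collect code instead of a bare tick in Protocol Table 2 would also remove doubt.
3. State in SAP 11.1.3 that the Early Withdrawal diary is entered before the event or censoring date is set.

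A medication review at this visit is an optional addition, not a correction.

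The cost is one line in 7.8, one or two table cells and one sentence in the SAP. The visit and the Diary Summary form already exist, and no treatment is affected. The change recovers nothing for subjects with no Early Withdrawal visit: those who die, and those lost to follow-up or withdrawing consent, for whom 7.8 does not insist on the visit. Their number should be reported beside the Kaplan-Meier estimate.

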7.9 Handling of Lost-to-Follow-up Subjects

Every attempt must be made to have all subjects complete the follow-up visit schedule. A subject will be considered lost-to-follow-up when all efforts to obtain compliance are unsuccessful. At a minimum, the effort to obtain follow-up information must include three attempts to make contact via telephone and if contact via phone is not successful, a certified letter from the principal investigator (PI) or authorized delegate must be sent to the subject's last known address. Both telephone and letter contact efforts to obtain follow up must be documented in the subject's medical records and on the Study Completion case report form (CRFs).

8 MEASURES TO AVOID AND MINIMIZE BIAS

The study has several measures that have been implemented to avoid and minimize bias, namely, establishment of an independent Data Safety Monitoring Board (DSMB), Clinical Events Committee (CEC), and the use of an MRI core laboratory.

8.1 Data Safety Monitoring Board

The DSMB will be a group comprised of individuals who are independent of the Sites. The board will be comprised of representatives from multiple disciplines including but not limited to epilepsy, neurosurgery, and biostatistics/epidemiology.

The board will establish a DSMB charter which will contain data monitoring criteria for the study, including frequency of meetings, review of aggregate data, and stopping rules if safety concerns arise from their review of the study data.

8.2 Clinical Events Committee

The CEC will be a group comprised of individuals who are independent of the Sites. The board will be comprised of representatives from multiple disciplines including but not limited to epilepsy and neurosurgery.

The Committee will establish adjudication guidelines governing their periodic review and adjudication of adverse events to assure appropriate and consistent classification.

8.3 MRI Core Laboratory

An MRI core laboratory will be used to provide an unbiased assessment of MRI measures, including brain tissue response to LITT and volume of the lesion.

A core laboratory charter will outline image acquisition and processing, and other functions of the core laboratory.

9 ADVERSE EVENTS

9.1 Definitions

Adverse Event

An adverse event (AE) is any untoward medical occurrence, unintended disease or injury, or untoward clinical signs whether or not related to the investigational medical device. This includes events related to the medical device and events related to the procedures involved.

Disease signs and symptoms that existed prior to study participation are not considered AEs unless the condition worsens in intensity or frequency during the study.

Collection of AEs will start on the day of the procedure and will be assessed and reported throughout the study. Investigators must obtain all information available to determine the causality and outcome of the AE and to assess whether it meets the criteria for classification as a serious adverse event (SAE) requiring immediate notification to the Sponsor or CRO. All reported AEs will be documented on the CRF. All AEs will be followed until resolution or PI determination that the subject's condition is stable.

The following are not considered adverse events for this study:

- Any normal expected postoperative complaints or symptoms unless the event involves a clinically significant change in severity or duration of symptoms, or requires clinical intervention that is different from ordinary postoperative care. Expected postoperative complaints and findings include, but are not limited to: headache, edema (on MRI), nausea and vomiting, and postoperative pain.
- Any condition that is recorded as pre-existing on the Baseline CRF, unless there is a worsening of that condition in terms of nature, severity, or degree of incidence.
- Planned hospitalization for a pre-existing condition or a procedure required by the protocol, without serious deterioration in health.

Adverse Device Effect

An adverse device effect (ADE) is an AE related to the use of the study device.

This definition includes AEs resulting from insufficient or inadequate instructions for use, deployment or operation, or any malfunction of the medical device. This definition also includes any event from an error in usage or from intentional misuse of the medical device.

Serious Adverse Event

A serious adverse event (SAE) is an AE that:

- Led to death;
- Led to serious deterioration in the health of the subject, that resulted in:
 - a life-threatening illness or injury, or

- a permanent impairment of a body structure or a body function, or
- hospital admission (>24 hours) or prolongation of an existing hospitalization, or
- medical or surgical intervention to prevent permanent life-threatening illness or injury, or permanent impairment to a body structure or a body function;
- Led to fetal distress, fetal death or a congenital anomaly or birth defect

Note: An adverse event is considered “life-threatening” if, in the view of either the investigator or Sponsor, its occurrence places the subject at immediate risk of death. It does not include an adverse event that, had it occurred in a more severe form, might have caused death.

Planned hospitalization for a pre-existing condition, or a procedure required by the protocol, without serious deterioration in health, is not considered an AE or an SAE.

Serious Adverse Device Effect

A serious adverse device effect (SADE) is an adverse device effect that has resulted in any of the consequences characteristic of a serious adverse event.

Anticipated Serious Adverse Device Effect

An anticipated serious adverse device effect is an effect which by its nature, incidence, severity or outcome, has been identified in the risk analysis report.

Unanticipated Serious Adverse Device Effect

An unanticipated serious adverse device effect (USADE) is a serious adverse effect, which by its nature, incidence, severity or outcome, has not been identified in the current version of the risk analysis report, protocol or application (including a supplementary plan or application). USADEs are also commonly called unanticipated adverse device effects (UADE), as defined in 21 CFR 812.3 (s).

Device Malfunction

A device malfunction is defined as a failure of an investigational medical device to perform in accordance with its intended purpose when used in accordance with the IFU or protocol.

AE Severity

The severity of an adverse event is a qualitative judgment of the degree of intensity, as determined by the PI. The severity of the adverse event should be evaluated according to the following scale:

- **Mild:** Does not interfere in a significant manner with the subject's normal functioning level.
- **Moderate:** Produces some impairment of functioning but is not hazardous to health.
- **Severe:** Produces significant impairment of function or incapacitation and is a hazard to the subject's health.

The assessment of severity should be made independent of the relationship to the device and therapy or the seriousness of the event.

AE Relationship

The investigator will assess the relationship of the adverse event to the device treatment or procedure as follows:

- **Definite** – The adverse event follows a strong temporal sequence to the receipt (or attempted receipt) of the device treatment or procedure. This can include an adverse event that occurs after the study procedure.
- **Probable** – The adverse event follows a reasonable temporal sequence to the receipt (or attempted receipt) of the device treatment or procedure, and the possibilities of other factors, such as underlying and concomitant illness, concomitant medications, or concurrent treatment can be excluded.
- **Possible** – The adverse event follows a reasonable temporal sequence from receipt (or attempted receipt) of the device treatment or procedure and the possibility of device treatment or procedure involvement cannot be excluded. However, other factors such as underlying or concomitant illness, concomitant medications, or concurrent treatment are presumable.
- **Unlikely** – The adverse event has an improbable temporal sequence to the receipt (or attempted receipt) of the device treatment or procedure, or it can be reasonably explained by other factors, including underlying or concomitant illness, concomitant medications, or concurrent treatment.
- **Not Related** – The adverse event has no temporal sequence to the LITT procedure, NeuroBlate System or any user handling, or it can be explained by other factors, including underlying disease or concomitant illness, concomitant medication, or concurrent treatment.

If the event was assessed by the investigator as *unlikely* or *not-related* to the study device treatment or procedure, one of the following alternate causations will be recorded:

- **New illness/injury:** Event is a new illness or injury that is not part of the subject's baseline medical history.
- **Pre-existing condition/disease:** Event is a worsening or exacerbation of a pre-existing condition/disease (such as epilepsy or other items listed in the baseline medical history).
- **Anesthesia:** Event is related to anesthesia.
- **Epilepsy medication:** Event has a strong temporal relationship to an epilepsy medication.
- **Non-epilepsy medication:** Event has a strong temporal relationship to a non-epilepsy medication.
- **Unknown:** Event relationship is not known or unsure.

